#### **1.3.3 Safety Analysis**

Safety will be assessed using the SAF.

##### **1.3.3.1 The number and proportion of subjects with AEs**

Adverse Events will be coded using the MedDRA classification to give a preferred term and primary system organ class for each event. Proportions of subjects with adverse events will be presented by treatment group. Tables of AEs will be presented by system organ class, and preferred term, and include overall totals for AEs within each system organ class. Counting will be done by subject and not by event. A table of counts and percentages will also be made of those subjects with SAEs or AEs which led to withdrawal from the study.

Treatment-emergent AEs are defined as adverse events that had an onset day and time on or after the day and time of the first dose of study drug up to 30 days after the last application of treatment. Adverse Events having missing onset dates will be considered as treatment emergent.

Worsening of pouchitis will be evaluated as a separate event.

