#### **Safety Set**

The safety analysis (SAF) set will consist of all randomized subjects who took at least a part of one dose of study drug, and will be used for all analyses of safety.

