#### **1.3.4 OPEN LABEL ACCESS ANALYSIS**

The following safety analysis will be conducted in all subjects receiving at least a part of one dose

1. The number and proportion of subjects with AEs; (worsening of disease will also be evaluated separately)
2. Assessment of clinical laboratory parameters
3. Assessment of vital signs

The following efficacy analysis will be conducted in all subjects receiving at least 80% of a 42-night treatment course

1. Percentage of subjects who report response to open-label access alicaforsen.
2. Interval between previous and current treatment courses

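### The treatment-emergent AE definition leaves out pre-dose events that worsen on drug, counts undated events known to have ended before dosing, and sets no boundary at open-label dosing

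*SAP*

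**What the plan says.** Section 1.3.3.1 of the SAP defines treatment-emergent events as "adverse events that had an onset day and time on or after the day and time of the first dose of study drug", and closes the window at "up to 30 days after the last application of treatment". For incomplete records it has one rule: "Adverse Events having missing onset dates will be considered as treatment emergent". The only reference to worsening in that section is "Worsening of pouchitis will be evaluated as a separate event". On presentation it says "Proportions of subjects with adverse events will be presented by treatment group".

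The population is set out under Safety Set: "The safety analysis (SAF) set will consist of all randomized subjects who took at least a part of one dose of study drug".

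Section 1.3.4 then gives open-label access its own adverse event analysis: "The following safety analysis will be conducted in all subjects receiving at least a part of one dose". It describes the open-label course only through the threshold for its efficacy analysis, "at least 80% of a 42-night treatment course". It does not say when open-label dosing may start relative to the randomised course, nor to which phase an event belongs.

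**The concern.** A treatment-emergent definition decides which events are read as possibly caused by dosing. This one has two clear faults and one gap.

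- **Worsening.** With onset as the only criterion, a condition present before dosing that becomes more severe on drug never qualifies. The SAP sees that worsening matters, since it singles out pouchitis, but makes no provision for any other condition.
- **Undated events.** Counting an event as emergent when its timing is unknown is a sound conservative default. The rule goes further and also counts an event whose end date shows that it was over before the first dose. Such an event cannot be emergent.
- **Phase boundary.** The window opens at the first dose of study drug but closes by reference to treatment in general. For a subject who goes on to open-label alicaforsen, a programmer must decide whether the last application is the last randomised or the last open-label one. If the window reaches into open-label dosing, a placebo subject's events on open-label alicaforsen could be tabulated under placebo and again under 1.3.4.

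At stake is a clean attribution of events to randomised treatment. No efficacy conclusion is touched.

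**Working it through.** The SAP states no figure to reproduce, so the check applies the rules of 1.3.3.1 to example records and then looks at where the window ends.

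**Step 1: the definition applied literally**

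| Record | Result under 1.3.3.1 | What the dates show |
|---|---|---|
| Onset before first dose, mild; severe after first dose | Not emergent (onset too early, no worsening clause) | Worsened on drug |
| Onset missing; end date before first dose | Emergent (missing-date rule, no exception) | Over before dosing |
| Onset missing; end date after first dose or unknown | Emergent | Timing uncertain; the default is reasonable |
| Onset during an open-label course | Depends on what the last application means and on timing | Arose on open-label alicaforsen |

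The first two results follow from the text and need no assumption. Nothing elsewhere in the SAP changes them. The shift tables in 1.3.3.2 and 1.3.3.3 can show worsening of laboratory values and vital signs, but they do not reclassify adverse events.

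**Step 2: where the window ends**

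The SAP gives 42 nights for the open-label course only. Assume the same length for the randomised course, with the first dose on day 1.

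- Randomised treatment only: last dose on day 42, window ends on day 42 + 30 = day 72.
- Any treatment, open-label start assumed on day 71: last dose on day 71 + 41 = day 112, window ends on day 112 + 30 = day 142.
- Any treatment, open-label start assumed on day 183: last dose on day 183 + 41 = day 224, window ends on day 224 + 30 = day 254.

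Both start days are illustrations; the SAP states neither. On the narrow reading, a start on day 71 overlaps the randomised window on days 71 and 72 only, and a start on day 183 does not overlap it at all. On the broad reading, the randomised window covers the whole open-label course in both cases.

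**Step 3: which reading the text favours**

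For the narrow reading: the sentence stands in the randomised safety section, starts from the first dose of study drug, and feeds tables by treatment group, while open-label access has its own section. For the broad reading: the word treatment is unqualified here, 1.3.4 also calls open-label dosing a treatment course, and the pouchitis intervention analysis in 1.3.2.2 uses the more specific term study treatment. The narrow reading is the more natural, but the SAP does not settle it.

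**The case against.** The strongest replies are these.

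**The open-label gap comes down to a missing adjective.** This largely stands. If treatment means the randomised course, overlap arises only when open-label dosing starts within 30 days of the last randomised dose. The SAP does not give that timing, and the protocol, not shown, may. What remains is that no rule assigns an event to one phase.

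**The undated-event rule is conservative and the same in both arms.** True, and the default should stay. The fault is only the missing exception. How often it matters depends on when adverse event collection starts, which the SAP does not say.

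**Worsening may be captured elsewhere.** If the protocol has a worsened pre-dose event recorded as a new event with a new onset date, it would enter the window. That would soften the point, but the SAP's definition does not say so.

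**Details of this kind are settled later.** SAP section 1 foresees a detailed plan before database lock, and section 1.4 lists finalisation of the SAP at the blinded review. That is a good time to correct the rule. It does not make the present text right, since this document chose to state both the definition and the missing-date rule.

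Two stronger inferences are tempting, and the document supports neither.

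- A reader might infer that reported harm will be understated. But 1.3.3.1 does not say that its tables are restricted to treatment-emergent events, so an event outside the definition may still be tabulated.
- A reader might infer that open-label events in placebo subjects would greatly shrink the difference between arms. Any such figure needs invented rates and depends on which arm is assumed to be affected. Suppose 30% of 69 alicaforsen subjects (20.7) and 10% of 69 placebo subjects (6.9) have an event, and 20 placebo subjects go open-label, 18 of them event-free. Placebo becomes (6.9 + 18 × 0.30)/69 = 17.8%, and the 20-point difference falls to 12.2. But the same window would run on for alicaforsen subjects. With 20 entering, 14 of them event-free, that arm becomes (20.7 + 14 × 0.30)/69 = 36.1%, and the difference is 18.3. The SAP supplies neither the event rates nor the uptake, so neither result is an estimate for this trial.

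**Conclusion.** The concern holds in a limited form. Read as written, the definition wrongly excludes pre-dose events that worsen after the first dose and wrongly includes undated events whose end date precedes it. These two faults rest on the text alone, subject to how the protocol has worsening recorded. The missing cut at open-label dosing is a weaker, conditional point: it matters only if open-label dosing starts within 30 days of the last randomised application, or if the last application is taken to include open-label doses. The SAP settles neither.

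Opening the window at the first dose is not itself at fault. The effect is probably a few events and cannot be quantified from the SAP. The correction is worth making because it is cheap and because the present wording allows different derivations.

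**What to change.** Revise section 1.3.3.1 before unblinding, at the latest when the SAP is finalised at the blinded review:

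1. Define a treatment-emergent event as one that starts, or worsens in severity, on or after the first randomised dose.
2. Keep a missing onset date as emergent by default, unless the end date or the known part of the onset date places the event before the first dose or after the window.
3. End the window at the earlier of 30 days after the last randomised application and the first open-label dose, and assign later events to the analysis in 1.3.4.

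The cost is SAP wording and a little derivation work. No new data are needed, provided the adverse event record shows changes in severity, which the SAP does not state. The treatment-emergent count may change slightly: up from worsened events, down from undated events shown to be pre-dose.

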##### **1.3.3.2 Laboratory Parameters**

The number (%) of subjects with abnormal values post-baseline will be tabulated by treatment group. In addition, summary statistics (i.e., mean, minimum, maximum, standard deviation, and number of subjects) will be presented for each treatment group for each laboratory parameter at each visit. When calculating the summary statistics only, the last observation within a visit window will be used if there are multiple observations. Changes from baseline will be presented in a similar format. An additional listing will be provided of those subjects who have clinically significant laboratory values. The data will also be presented as shift tables and clinically significant abnormalities will also be examined.

##### **1.3.3.3 Vital Signs**

Abnormal vital signs will be counted by treatment group. The number (%) of subjects with any post-baseline vital sign readings above and/or below the specified levels will be presented for each treatment group. In addition, summary statistics (i.e., mean, minimum, maximum, standard deviation, and number of subjects) will be presented for each treatment group for each vital sign at each visit, comparing changes from baseline. When calculating the summary statistics only, the last observation within a visit window will be used if there

are multiple observations. The data will also be presented as shift tables and clinically significant abnormalities will also be examined.

#### **1.3.3.4 Withdrawals**

The number (%) of subjects who withdraw from the study and their reasons for withdrawal will be tabulated by treatment group. The distribution of withdrawals and reasons will also be displayed at each visit by treatment group

#### **1.3.4 OPEN LABEL ACCESS ANALYSIS**

The following safety analysis will be conducted in all subjects receiving at least a part of one dose

1. The number and proportion of subjects with AEs; (worsening of disease will also be evaluated separately)
2. Assessment of clinical laboratory parameters
3. Assessment of vital signs

The following efficacy analysis will be conducted in all subjects receiving at least 80% of a 42-night treatment course

1. Percentage of subjects who report response to open-label access alicaforsen.
2. Interval between previous and current treatment courses

#### **1.4 BLINDED DATA REVIEW MEETING**

The Sponsor will convene a Blinded Data Review Meeting after the data has been cleaned but before the study is unblinded. The review will be performed within the framework of the requirements of the ICH Guideline E9.

The terms of reference for the Data Review Meeting will include, but will not be limited to:

- the determination of whether protocol violations are 'major' or 'minor', or not a protocol violation at all;
- the allocation of subjects to analysis sets;
- a review of missing data and of outliers;
- a review of the distribution of the efficacy variables, considering any implications for the proposed method of statistical analysis;
- an assessment of the overall endoscopic remission rate;
- a review of whether additional covariates need to be included in the analyses;
- the finalisation of the SAP.

If the overall endoscopic remission rate indicates that the assumptions of the sample size calculation were not realized during the study then the Sponsor, taking the advice of the Data Review Meeting, may make one or more of the following changes to the primary analysis:

- changing the definition of the analysis set used;
- changing the definition of the primary endpoint;
- any other change deemed by the Sponsor as necessary to preserve the integrity of the study.

All persons taking part in the Data Review Meeting and all persons taking part in any deliberations concerning the format of the primary analysis must remain blinded to treatment allocation until any changes to the protocol specified analyses are documented and signed-off.

Formal records shall be kept of when the statistical analysis plan was finalized as well as when the blind was subsequently broken.

#### **1.4.1 PK Parameters**

Plasma PK parameters for alicaforsen will be evaluated as follows. All consenting subjects will provide single time-point plasma samples at Day 1, Week 3 and Week 6.

In addition, full plasma concentration-time curves will be generated from a subset of randomised subjects (24 subjects, approximately 12 on active treatment and 12 on placebo) at Day 1 and Week 6. Samples from subjects in the placebo group will NOT be analyzed.

In this subset of subjects, the following PK parameters, as a minimum, will be calculated for alicaforsen:  $C_{max}$ ,  $t_{max}$ ,  $t_{1/2}$ ,  $AUC_t$ ,  $AUC_{0-24}$ ,  $AUC_{0-\infty}$ , and  $\lambda_z$ .

The following pharmacokinetic parameters will be derived:

$C_{max}$	The peak plasma concentration.
$t_{max}$	The time of peak plasma concentration.
$t_{1/2}$	The terminal half-life calculated from the terminal slope of the log concentration-time curve.
AUC	The area under the concentration-time curve will be calculated using the trapezoid rule for the interval 0 to $t_n$ h (time $t_n$ is the time at which the last non-zero level was recorded), plus the area under the exponential curve from $t_n$ h to infinity. The linear trapezoidal method will be used up to $t_{max}$ , and the logarithmic method will be used for the plasma concentrations declining from $C_{max}$ . The area from the time of last measured concentration to infinity will be extrapolated using the following formula:

$$AUC_{t_n-\infty} = \frac{\hat{C}_n}{\lambda_z}$$

where  $\lambda_z$  is the elimination rate constant calculated from non-linear regression of the terminal portion of the plasma concentration time curve, and  $\hat{C}_n$  is the predicted value of the concentration at time  $t_n$ .

Alicaforsen concentration-time curves will be plotted for individual subjects and will be summarized at Day 1 and Week 6, with concentrations on both log and linear scales. Single time-point PK data will be tabulated and summarized for each subject at Day 1, Week 3 and Week 6. Summary statistics for these data will also be computed across subjects.
